8.1.3 Patient Reported Outcomes

The handling of missing data for patient reported outcomes (PROs) will be as follows. The missing items of the FSS questionnaire will be imputed with the average score of the answered items as long as more than 50% of the items on the FSS are answered. For EQ-5D-3L index and VAS scores, no imputation will be performed for missing items.

The mean change from baseline will be summarized descriptively for the FSS total score and the EQ-5D-3L health index score and VAS score at each visit.

The cumulative number and percentage of subjects who have ever experienced an increase from baseline in the FSS total score of greater than or equal to 0.7 through each applicable time point will also be calculated.

The analyses described above will also be performed separately for each geographic region. Additional analyses of PROs will be performed as useful and appropriate.

8.1.4 HCV and HIV Resistance Analyses

For subjects who, experience virologic failure (on treatment virologic failure or post-treatment relapse), full length NS3/4A and NS5A genes from their available baseline samples will be sequenced by population or deep sequencing. For each DAA target, resistance-associated signature amino acid variants will be identified by AbbVie Clinical Virology. An appropriate prototypic reference sequence will be used for comparison with sequences from samples.

Only samples with an HCV RNA level of ≥ 1000 IU/mL will undergo sequence analysis in order to allow accurate assessment of products of amplification. Therefore, if the HCV RNA level at the time of virologic failure or treatment discontinuation is < 1000 IU/mL, the sample closest in time after failure/discontinuation with an HCV RNA level ≥ 1000 IU/mL will be used. Included time points for analyses on available samples from subjects who do not achieve SVR₁₂ are 1) the sample closest in time after failure/discontinuation with an HCV RNA level of ≥ 1000 IU/mL, and 2) 24 weeks post-DAA treatment, provided that resistance-associated substitutions were detected by either population or deep sequencing at the time of failure/discontinuation.

The following definitions will be used in the resistance analyses:

- Baseline variant: a variant (by population or deep sequencing) in a baseline sample determined by comparison of the amino acid sequence of the baseline sample to the appropriate prototypic reference amino acid sequence for a given DAA target.
- Post-baseline variant by population or deep sequencing: an amino acid variant detected by population or deep sequencing in a post-baseline time point sample that was not detected by population or deep sequencing at baseline in the subject.
- Emerged variant by population or deep sequencing: a post-baseline variant that is observed in 2 or more subjects of the same HCV sub-genotype by population or deep sequencing.

The following analyses will be performed for all subjects who experience virologic failure:

The HCV amino acid sequence as determined by population or deep sequencing of available baseline samples will be compared to the appropriate prototypic reference amino acid sequence. A listing by subject of all baseline variants relative to prototypic reference sequence at signature resistance associated amino acid positions will be provided for each DAA target (NS3 and NS5A).

The following analyses will be performed for subjects who experience virologic failure and have post-baseline resistance data available:

The HCV amino acid sequence as determined by population or deep sequencing on the sample closest in time after virologic failure with an HCV RNA level of ≥ 1000 IU/mL will be compared to the baseline and appropriate prototypic reference amino acid sequence. Listings by subject of all post-baseline variants detected by population or deep sequencing relative to the baseline amino acid sequences will be provided for each DAA target (NS3 and NS5A). Listings by subject of all emerged variants by population or deep sequencing, by amino acid position and variants within a DAA target in a post baseline sample relative to the baseline amino acid sequence will be provided for each DAA target. In addition, listings by subject of all post-baseline amino acid variants (by population or deep sequencing) at signature resistance associated positions relative to the appropriate prototypic reference amino acid sequence will be provided for each DAA target (NS3 and NS5A).

The persistence of post-baseline variants at signature resistance-associated amino acid positions for each target (NS3 and NS5A) will be assessed by population or deep sequencing at Post-Treatment Week 24. Listings by subject and time point of all post-baseline variants relative to the baseline amino acid sequence will be provided for each DAA target (NS3 and NS5A).

If resistance-associated substitutions are not detected by either population or deep sequencing in a given target for a subject at the time of failure, then that target may not be sequenced in subsequent samples from that subject.

HIV-1 drug resistance genotyping for protease, reverse transcriptase and integrase may be performed for protocol defined eligible specimens.

8.1.5 Safety

All subjects who receive at least one dose of study drug will be included in the safety analyses. Safety data will be summarized for the set of all subjects, separately for each geographic region, and for the set of HCV/HIV co-infected subjects.

8.1.5.1 Adverse Events

Adverse events (AEs) will be coded using the Medical Dictionary for Regulatory Activities (MedDRA). The number and percentage of subjects with treatment-emergent AEs (i.e., any event that begins or worsens in severity after initiation of study drug through 30 days post-study drug dosing) will be tabulated by primary MedDRA System Organ Class (SOC) and preferred term. The tabulation of the number of subjects with treatment-emergent AEs by severity grade and relationship to each study drug (DAAs) also will be provided. Subjects reporting more than one AE for a given MedDRA preferred term will be counted only once for that term using the event with the most severe grade from the severity grade table and the most related event from the relationship to study drug tables. Subjects reporting more than one type of event within a SOC will be counted only once for that SOC.

8.1.5.2 Clinical Laboratory Data

Clinical laboratory test values will be summarized at each visit. The baseline value will be the last non-missing measurement prior to the initial dose of study drug. Mean changes from baseline to each post-baseline visit, including Final Treatment Visit, will be summarized descriptively.

Laboratory data values will be categorized as low, normal, or high based on reference ranges of the laboratory used in this study. Shift tables from baseline to minimum value and from baseline to maximum value will be created. The shift tables will cross-tabulate the frequency of subjects with baseline values below/within/above the normal range versus minimum/maximum post-baseline values below/within/above the normal range.

In addition, the number and percentage of subjects with post-baseline values during the Treatment Period meeting pre-specified criteria for potentially clinically significant laboratory values or toxicity grades will be calculated.

8.1.5.3 HIV-1 RNA Data

For the HCV/HIV co-infected subjects who were on stable HIV-1 ART at initiation of study drug, the number and percentage of subjects with 2 consecutive HIV-1 RNA values ≥ 200 copies/mL during the Treatment Period will be calculated.

8.1.5.4 Vital Signs Data

Mean changes in temperature, systolic and diastolic blood pressure, pulse, and weight from baseline to each post-baseline visit, including Final Treatment Visit, will be summarized descriptively. The number and percentage of subjects with post-baseline values meeting pre-defined criteria for potentially clinically significant vital signs values will be summarized.

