- A complete medical history will be taken at Screening and will be updated at the Screening Visit.
- Height will be measured at the Screening Visit only. Waist circumference will be measured at the Screening Visit, but if it is not measured at Screening, it may be measured on Day 1.
- Only at Screening, for female subjects to assess postmenopausal state.

- g. Pregnancy testing is not required for females of non-childbearing potential as defined in Inclusion Criterion 3.
- h. Perform the test for HBV DNA if HBsAg is negative.
- i. For those with history of diabetes mellitus.
- j. For subjects who have not had a qualifying liver biopsy within the previous 24 months or a qualifying FibroScan[®] within the previous 6 months.
- k. If the sample is not collected at Study Day 1, it may be collected at any other visit during the study.
- l. See specific information regarding adverse event collection in Section 6.1.4.
- m. PROs should be administered before any study procedures. EOT PROs are at Week 12 EOT or Week 16 EOT, as applicable.
- n. Applicable only to those subjects enrolled into a 16-week treatment.
- o. Subjects should bring all the study drug to the study drug accountability visits at Weeks 4, 8, 12, EOT or Premature D/C. The site will record the number of tablets returned only at these visits.
- p. HCV/HIV co-infected subjects only.
- q. For HCV/HIV co-infected subjects on stable ART: As detailed in Section 5.4.1.2, a repeat HIV-1 RNA blood draw to confirm a HIV-a RNA result of ≥ 200 copies/mL can be done as an unscheduled visit, but must be performed at least 2 weeks apart from the prior HIV-1 RNA result. At the time the repeat plasma HIV-1 RNA is drawn, a sample may be obtained for HIV-1 resistance testing. If the confirmatory HIV-1 RNA lab draw falls on the date of a scheduled study visit, only a single HIV-1 RNA and HIV-1 resistance blood draw is needed at the visit.
- r. Details regarding timing of PK samples are provided in Section 5.3.2.1.
- s. For subjects participating in Optional Intensive PK sampling, additional PK samples will be drawn on Study Day 1 at 2, 4 and 6 hours post-dose and on Week 4 visit immediately prior to dose (0 hour) and 2 and 4 hours post-dose during the visit.

Study Activities – Post Treatment Period

Activity	PT Week 4	PT Week 12	PT Week 24 or PT D/C ^a
Vital Signs and Weight	X	X	X
Hematology/Chemistry/Urinalysis/Coagulation Panel	X		X ^b
Pregnancy Test (urine) ^c	X (u)		X (u) ^b

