c. The last value within the window will be used to define the Final Treatment Visit value. The upper bound of this Final window is Study Drug End Day 2. Study Drug End Day 0 is defined as the day of the last dose of study drug.

Note: For all windows, data must be on or before Study Drug End Day 2. The result closest to the scheduled time point will be used. PRO instruments are collected at Day 1, Week 4 and End of Treatment Visit; Total insulin, Child-Pugh score and alpha fetoprotein are collected at Day 1 and End of Treatment Visit.

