#### 11.4.2 Statistical Methods

The baseline value for vital signs will be the last measurement on or before the day of the first dose of study drug. The same baseline value will be used for all summaries of the data from the Treatment and Post-Treatment Period visits.

Changes from baseline to each post-baseline visit, including applicable post treatment visits, will be summarized. Each vital sign parameter will be summarized with the baseline mean; visit mean; and change from baseline mean, standard deviation, minimum, median, and maximum.

The number and percentage of subjects with on-treatment values meeting the specified criteria for PCS vital sign values (Table 12) will be calculated. A post-baseline value must be more extreme than the baseline value to be considered a PCS finding. A separate listing will be provided that presents all vital sign values for the subjects meeting PCS criteria during treatment.

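### The SAP limits the count of potentially clinically significant vital signs to on-treatment values, where the protocol counts all post-baseline values, and does not declare the change

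*Protocol*

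**What the plan says.** Protocol 8.1.5.4, on vital signs: "The number and percentage of subjects with post-baseline values meeting pre-defined criteria for potentially clinically significant vital signs values will be summarized". Two subsections earlier, Protocol 8.1.5.2 handles the parallel laboratory count differently and takes "post-baseline values during the Treatment Period meeting pre-specified criteria for potentially clinically significant laboratory values or toxicity grades will be calculated".

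SAP 11.4.2 gives the vital-sign rule as: "The number and percentage of subjects with on-treatment values meeting the specified criteria for PCS vital sign values (Table 12) will be calculated". The listing follows the same selection: "A separate listing will be provided that presents all vital sign values for the subjects meeting PCS criteria during treatment". The same section also specifies a by-visit summary: "Changes from baseline to each post-baseline visit, including applicable post treatment visits, will be summarized". Its statistics include "change from baseline mean, standard deviation, minimum, median, and maximum".

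SAP 11.4.2 does not itself define on-treatment. The note to SAP Table 1, which governs vital signs in the Treatment Period, says: "For all windows, data must be on or before Study Drug End Day 2". SAP 11.3.2 uses the same cut-off for laboratory shift tables.

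The post-treatment part of Protocol Appendix C has a row "Vital Signs and Weight" marked at PT Weeks 4, 12 and 24 (or PT discontinuation). SAP Table 3 assigns analysis windows to these measurements and leaves PT Week 24 out of the primary CSR.

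**The concern.** The two documents define different counts under the same name. The protocol's version takes in the whole period after baseline; the SAP's version stops two days after the last dose. Someone reading the study report against the protocol would take the PCS table to cover follow-up, and nothing in SAP 12.1 would correct that.

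Safety is a primary objective, every subject has cirrhosis, and Protocol 5.1 gives safety monitoring as one purpose of the 24-week follow-up. Under Protocol 6.1.4, nonserious adverse events are no longer collected once 30 days have passed after treatment. A nonserious PCS value first seen at PT Week 12 or 24 would thus not be recorded as an adverse event either. Scheduled measurements are the main way it would be seen, and the SAP leaves those measurements out of the PCS count.

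**Working it through.** The plan states no figure for this count, so there is nothing to reproduce. The check compares the texts and then counts scheduled visits.

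**1. Does post-baseline mean on-treatment in these documents?**

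| Place | Values used | Treatment-period limit stated? |
|---|---|---|
| Protocol 8.1.5.2, PCS or graded laboratory values | post-baseline | yes |
| Protocol 8.1.5.3, HIV-1 RNA | two consecutive values at or above 200 copies/mL | yes |
| Protocol 8.1.5.4, PCS vital signs | post-baseline | no |
| SAP 11.4.2, PCS vital signs | on-treatment | yes |

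The protocol adds the limit in the two preceding subsections and omits it for vital signs. SAP 11.4.2 itself treats post-treatment visits as post-baseline visits in its change-from-baseline sentence. The natural reading is that the terms differ and that the SAP narrows the count.

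**2. Is the narrowing declared?** None of the 16 items in SAP 12.1 concerns PCS vital signs. The list is otherwise detailed: item 10 records the removal of a single word from a fatigue analysis.

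**3. How many scheduled visits are left out?** The on-treatment visits come from the Protocol synopsis and the post-treatment visits from Appendix C.

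- 12-week regimen: Weeks 1, 2, 4, 8, 12 = 5 on treatment; PT Weeks 4, 12, 24 = 3 after. Share left out = 3/(5 + 3) = 3/8 = 37.5%.
- 16-week regimen: 6 on treatment, 3 after. Share left out = 3/(6 + 3) = 3/9 = 33.3%.
- In the primary CSR, without PT Week 24: 2/(5 + 2) = 2/7 = 28.6% and 2/(6 + 2) = 2/8 = 25%.

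**4. Which way can the count move?** Every on-treatment value is also a post-baseline value. Hence:

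protocol count = SAP count + number of subjects whose only Table 12 values are post-treatment.

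The last term is zero or more, so the SAP count is at most the protocol count.

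**5. Can the by-visit minimum and maximum stand in for the count?** Table 12 requires an absolute level together with a change for blood pressure and pulse. For weight it requires a change of at least 15%. Take a 60 kg subject who weighs 70 kg at PT Week 12: 70/60 = 1.167, a gain of 16.7%, which meets the criterion. The threshold for this subject is 0.15 × 60 = 9 kg. The 10 kg gain might be the maximum printed for that visit, but a heavier subject could gain more kilograms while staying below 15%. For systolic pressure, the largest fall may belong to a subject who remains above 90 mmHg. The extremes therefore give neither the number of subjects meeting Table 12 nor their identity.

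**The case against.** The best defence is that the SAP follows a consistent convention. Laboratory shifts, toxicity grades and hepatotoxicity criteria are all restricted to treatment in SAP 11.3, and an on-treatment table is a reasonable choice when the interest is in effects attributable to the drug. The protocol wording is also not watertight: the first sentence of 8.1.5.4 names the Final Treatment Visit but no post-treatment visit. The laboratory shift tables in Protocol 8.1.5.2 likewise use post-baseline values without a stated limit, and the SAP limits those too. This makes the SAP's choice understandable. It does not make the two texts agree, and it does not explain the silence of SAP 12.1.

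Other reporting covers part of the ground. Child-Pugh scores are tabulated after treatment (SAP 11.5). Vital-sign changes that need intervention, or that the investigator judges to be adverse events, are collected as such for 30 days after dosing. All serious adverse events are listed through the end of study.

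A reader might go further and infer that extreme post-treatment values are never reported, or that the listing shows on-treatment values only. The documents do not support either. The by-visit summary covers post-treatment visits with a minimum and maximum change, and the listing, once a subject is selected, shows all of that subject's vital-sign values. A reader might also take the share of follow-up time after treatment (168 of 252 days for 12-week subjects) as the scale of the loss. It is not: PCS status is assessed at visits, and neither visits nor days count missed events.

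**Conclusion.** The discrepancy stands in a limited form. A subject whose only Table 12 value occurs after Study Drug End Day 2 is neither counted nor individually listed as PCS, contrary to the protocol wording. This concerns PT Weeks 4 and 12 in the primary CSR and PT Week 24 in the final CSR.

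The number of such subjects cannot be derived from the documents and may be zero. It would be wrong to say that the reported count will be lower; it can be lower and cannot be higher. The conclusion assumes that on-treatment in SAP 11.4.2 carries the same Study Drug End Day 2 limit as SAP Table 1, and that post-baseline in Protocol 8.1.5.4 carries its ordinary meaning.

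The study is single-arm and descriptive. SVR12 and the adverse event tables are unaffected, so this is a minor safety-reporting point.

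**What to change.** In SAP 11.4.2, keep the on-treatment count and add a separate count of subjects meeting Table 12 at any post-baseline value, including the post-treatment visits. Extend selection for the PCS listing to subjects who meet Table 12 at any post-baseline visit, and show the study period of each qualifying value.

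The cost is one more column and one listing condition, on data already collected and assigned to windows in SAP Table 3. The reported PCS count may rise slightly; keeping the on-treatment column separate preserves the view of effects during dosing.

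If the sponsor prefers the on-treatment restriction alone, an entry in SAP 12.1 should state it and give the reason. That removes the undeclared discrepancy but leaves subjects with only post-treatment findings uncounted.

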8.1.6 Pharmacokinetic and Exposure-Response Analyses

Plasma concentrations of ABT-530 and ABT-493 and possible metabolites and pharmacokinetic parameter values for ABT-493 and ABT-530 will be tabulated for each subject and group. Summary statistics will be computed for each time and visit.

Plasma concentration data from this study may be combined with data from other studies and analyzed using the following general methodology.

Population pharmacokinetic analyses will be performed using the actual sampling time relative to dosing. Pharmacokinetic models will be built using a non-linear mixed-effect modeling approach with the NONMEM software (version VII, or higher version). The structure of the starting pharmacokinetic model will be based on the pharmacokinetic analysis of data from previous studies. Apparent oral clearance (CL/F) and apparent volume of distribution (V/F) of the PK analytes will be the pharmacokinetic parameters of major interest in the NONMEM analyses. If necessary, other parameters, including the parameters describing absorption characteristics, may be fixed if useful in the analysis. The evaluation criteria described below will be used to examine the performance of different models.

- The objective function of the best model is significantly smaller than the alternative model(s).
- The observed and predicted concentrations from the preferred model are more randomly distributed across the line of unity (a straight line with zero intercept and a slope of one) than the alternative model(s).
- Visual inspection of model fits, standard errors of model parameters and change in inter-subject and intra-subject error.

Once an appropriate base pharmacokinetic model (including inter- and intra-subject error structure) is developed, empirical Bayesian estimates of individual model parameters will be calculated by the posterior conditional estimation technique using NONMEM. The relationship between these conditional estimates CL/F and V/F values with only potentially physiologically relevant or clinically meaningful covariates (such as subject age, sex, body weight, concomitant medications, laboratory markers of hepatic or renal function, etc.) will be explored using either stepwise forward selection method, or generalized additive method (GAM) or another suitable regression/smoothing method at a significance level of 0.05. After identification of all relevant covariates, a stepwise backward elimination of covariates from the full model will be employed to evaluate the significance (at $P < 0.005$, corresponding to an increase in objective function > 7.88 for one degree of freedom) of each covariate in the full model.

In general, all continuous covariates will be entered in the model, initially in a linear fashion, with continuous covariates centered around the median value. Linear or non-linear relationships of primary pharmacokinetic parameters with various covariates may also be explored. For example:

$$TVCL_i = \text{Theta}(1) + \text{Theta}(2) (\text{Comedication } [1,2,\dots]) + \text{Theta}(3) (\text{WT}_i - \text{median value}) + \text{Theta}(4) (\text{AGE}_i - \text{median value}).$$

Where $TVCL_i$ = Typical value of clearance for an individual, $\text{Theta}(1)$ is the intercept and $\text{Theta}(2) - (4)$ are regression parameters relating the fixed effects (weight and age centered on the median value) to clearance.

Relationship between exposure and clinical observations (antiviral activity) will be explored. Exposure-response relationships for primary and secondary efficacy variables and/or some safety measures of interest may also be explored.

The relationship between exposure (e.g., population pharmacokinetic model predicted concentrations over time or average concentrations or AUC or trough concentrations of the individual model-predicted pharmacokinetic profiles, or some other appropriate measure of exposure) and antiviral activity will be explored.

Logistic regression analyses will explore the relationship between exposure and one or more virologic endpoints (e.g., SVR_{12} , relapse following end of treatment and breakthrough on treatment).

Additionally, relationship between exposure and safety endpoints of interest may also be explored. Additional analyses will be performed if useful and appropriate.

